**c. Rationale for study**

When exacerbations of COPD that require hospitalization occur, short-acting bronchodilators (both beta agonists and anticholinergics) are routinely prescribed as part of a comprehensive regimen that includes supplemental oxygen, parenteral corticosteroids, antibiotics (usually), and if severe, non-invasive positive pressure ventilation.

According to GOLD 2018 recommendations, long-acting bronchodilators are to be introduced as soon as possible prior to discharge from the hospital if not continued during hospitalization. However, the recommendation to use short-acting bronchodilators as a primary therapeutic inhalant is based on grade C level of evidence, suggesting a paucity of data to support that position. Primarily related to pharmacy-driven cost considerations, the exclusive use of short-acting bronchodilators has become the standard of care in treating hospitalized patients with COPD exacerbations, with the introduction of long-acting inhalants only upon discharge, by a number of institutions including Ben Taub Hospital in Houston ([name]: personal communication), and throughout the Baylor Scott and White Healthcare System in Texas. This therapeutic substitution of short-acting for long-acting bronchodilators has been estimated to result in a cost savings of  $\sim$ \$400k at Baylor University Medical Center alone (personal

communication: director of pharmacy services). Even so, few if any studies have evaluated the length of stay, in-hospital adverse events (nocturnal awakenings related to respiratory symptoms that occur beyond the window of pharmacologic efficacy of short-acting medications), respiratory therapy utilization or the potential impact upon re-hospitalizations with this paradigm shift of care. Sanford Hospital System in North Dakota recently published a study comparing a once daily long-acting combination with compared with a twice-daily combination and saw minimal cost savings and no real change in outcomes. This same system had previously studied substitution of twice daily beta agonist and once daily anticholinergic bronchodilators for combination short-acting bronchodilators and found improved outcomes and cost savings but reported their results in a non-peer reviewed journal in (AARC Times, November 2011).

Results of an analysis of 60 patient charts randomly selected after hospitalization at Baylor University Medical Center for an exacerbation of underlying airways disease (>90% with COPD) showed tremendous variation in practice patterns; with 30% of patients receiving short-acting beta-antagonists and muscarinic agonists (SABA/SAMA) only, 70% receiving long-acting beta-antagonists (LABA) with PRN SABA/SAMA, and only 42% receiving a long-acting muscarinic agonist (LAMA), despite practice guidelines encouraging the use of SABA/SAMA only (typically 4 times daily and as needed).

It is this large variability that renders the evaluation and interpretation of institution-specific outcomes difficult. The main impetus for the proposed study is therefore to establish a more standardized open-label protocol which would allow for a more accurate assessment of intervention outcomes. As one of several secondary goals of this study, we aim to compare key outcomes (including, number of PRN treatments, length of hospital stay, and rate of readmission) with those from the historical cohort described above, when a combination LABA/LAMA/ICS inhaler is used as the primary scheduled daily inhaled therapy.

#### 4. PATIENT POPULATION

**a. Enrollment Goal**

This study aims to enroll 80 subjects. With an anticipated acceptance rate of 2/3, this means we will approach 120 eligible candidates over that period. We estimate we will be able to achieve 30-day follow-up in 80% of enrolled patients.

**b. Eligibility Criteria**

**i. Inclusion Criteria**

- a. Willing and capable of providing written informed consent.
- b. Subjects aged 18 years or older at time of enrollment.
- c. Diagnosis of COPD (per investigator's discretion by prior spirometry results or by spirometry assessment at screening visit) with or without asthma for  $\geq 12$  months.
- d. Hospitalized  $\leq 24$  hours prior to enrollment and currently hospitalized for COPD exacerbation with or without asthma.
- e. Able to properly use the Ellipta medication delivery device.
- f. Able to generate  $\geq 30$  L/min inspiratory flow rate (PIFR) at screening, measured with an InCheck DIAL adjusted to medium low resistance, to document a subject's ability to effectively inhale medication delivered via an Ellipta device.

**ii. Exclusion Criteria**

- a. Clinically significant lung disease other than COPD with or without asthma.
- b. Positive SARS-CoV-2 test at the time of ED or hospital admission, or any time between admission and enrollment.
- c. History of severe hypersensitivity to milk proteins or demonstrated hypersensitivity to fluticasone furoate, umeclidinium, vilanterol, or any of the excipients.
- d. Unable to perform inspiratory flow or spirometry procedures.
- e. Critically ill patients, or patients with rapidly deteriorating or life-threatening episodes of COPD or asthma including:
  - Patients in critical care unit, or transferred from critical care unit.

- Patients who are transferred to critical care after enrollment will be withdrawn from the study and continue to receive care according to institutional standard practice.
- Patients who initiate Bilevel Positive Airway Pressure (BiPAP) after hospitalization.
  - Patients who use BiPAP at baseline (prior to COPD exacerbation) may be included if BiPAP settings remain consistent with pre-exacerbation settings. Patients will be withdrawn if BiPAP settings are changed after enrollment.

f. Pregnant or lactating women or women of child-bearing potential (WOCBP). Women must meet the non-productive potential definition below to be eligible.

➤ Non-reproductive potential is defined as:

- Pre-menopausal females with one of the following:
  - Documented tubal ligation.
  - Documented hysteroscopic tubal occlusion procedure with follow-up confirmation of bilateral tubal ligation.
  - Hysterectomy.
  - Documented Bilateral Oophorectomy.
- Postmenopausal defined as 12 months of spontaneous amenorrhea with an appropriate clinical profile (e.g., age appropriate, >45 years, in the absence of hormone replacement therapy). In questionable cases for women <60 years of age, a blood sample with simultaneous follicle stimulating hormone and estradiol falling into the central laboratory's postmenopausal reference range is confirmatory. Females under 60 years of age, who are on HRT and whose menopausal status is in doubt, are required to use a highly effective method to avoid pregnancy if they wish to continue their HRT during the study. Otherwise, they must discontinue HRT to allow confirmation of postmenopausal status prior to study enrolment. For most forms of HRT, at

least 2 to 4 weeks will elapse between the cessation of therapy and the blood draw; this interval depends on the type and dosage of HRT. Following confirmation of their post-menopausal status, subjects can resume use of HRT during the study without use of a highly effective method to avoid pregnancy.

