#### **5.2.4 TREATMENT (Enrollment to Discharge)**

TRELEGY ELLIPTA (fluticasone furoate 100 mcg, umeclidinium 62.5 mcg, and vilanterol 25 mcg inhalation powder) will be initiated on the morning of enrollment if feasible, or the morning after enrollment otherwise. Treatment will continue daily until discharge. Treatments will be administered by a respiratory therapist daily in the morning between 06:00 AM and 12:00 PM. Patients will receive nebulized short-acting beta-2 agonist (SABA) treatments of albuterol sulfate (2.5mg) as needed during hospitalization. Patients will receive prednisone 40 mg PO daily for the first 7 days from enrollment, subtracting 1 day for each consecutive day the patient received systemic corticosteroid treatment prior to enrollment.

Treatment procedures/assessments include:

- Concomitant Medications
- AE Assessment
- TRELEGY administration

Data from the following specified assessments will be collected daily, when available, and entered the case report forms (CRFs):

- Vital Signs
- Short-acting beta agonist (SABA) therapy: number and time of treatments

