#### **5.2.6 30 DAY POST DISCHARGE/WITHDRAWAL FOLLOW-UP**

Subjects will receive a follow-up phone call from a study coordinator and Medical Charts will be reviewed to assess if the subject was readmitted within 30 days of discharge. Follow-up phone call and Medical Chart review will instead occur 30 days after withdrawal for patients who are withdrawn prior to discharge.

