## 6.4 COVID-19 CONSIDERATIONS

It is standard practice for patients admitted with respiratory symptoms to receive SARS-CoV-2 testing at the time of admission. The study will not require additional testing but will record results of any additional SARS-CoV-2 testing that occurs during hospitalization.

Patients with positive SARS-CoV-2 test at the time of admission or in the time between admission and enrollment will be excluded from the study. Patients with positive SARS-CoV-2 test after the time of enrollment will be withdrawn from the study and will continue to receive care according to institutional standard practice.

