## 6.5 PREGNANCY REPORTING

If pregnancy occurs in a female participant, the pregnancy should be reported as outlined below.

- Details of all pregnancies in female participants will be collected after the start of study intervention and until the safety follow-up visit.
- If a pregnancy is reported, the investigator will record pregnancy information on the appropriate form and submit it to the sponsor within 24 hours of learning of the pregnancy. While pregnancy itself is not considered to be an AE or SAE, any pregnancy complication or elective termination of a pregnancy for medical reasons will be reported as an AE or SAE.
- Abnormal pregnancy outcomes (e.g., spontaneous abortion, fetal death, stillbirth, congenital anomalies, ectopic pregnancy) are considered SAEs and will be reported as such.

- The participant will be followed to determine the outcome of the pregnancy. The investigator will collect follow-up information on the participant and the neonate, and the information will be forwarded to the sponsor.
- Any post-study pregnancy-related SAE considered reasonably related to the study intervention by the investigator will be reported to the sponsor as described in Section.
- While the investigator is not obligated to actively seek this information in former study participants, he or she may learn of an SAE through spontaneous reporting.
- Any female participant who becomes pregnant while participating in the study will discontinue study intervention but may remain in the study (if consent is not withdrawn).

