#### **e. Reporting and Exclusions**

Missing data will not be imputed or carried forward in any of the analyses.

The sample size for continuous variables will be the number of subjects with non-missing data; in the summary of categorical variables, subjects with missing data will be excluded in the calculation of percentages.

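### Patients who deteriorate are withdrawn from the study, and the plan does not say how their PRN, length-of-stay and readmission data are collected or analysed

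*Combined protocol and SAP*

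**What the plan says.** Three events after enrolment lead to withdrawal.

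- Critical care transfer (Section 4.b.ii item e, and the synopsis): "Patients who are transferred to critical care after enrollment will be withdrawn from the study", with care then following the hospital's usual practice.
- BiPAP change (same item): "Patients will be withdrawn if BiPAP settings are changed after enrollment". This sentence does not say from what.
- SARS-CoV-2 (Section 6.4): "Patients with positive SARS-CoV-2 test after the time of enrollment will be withdrawn from the study".

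The protocol can separate stopping treatment from leaving the study. Under Section 6.5 a participant who becomes pregnant "will discontinue study intervention but may remain in the study".

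PRN use is recorded daily in the period from enrolment to discharge (Section 5.2.4): "Short-acting beta agonist (SABA) therapy: number and time of treatments". Section 5.2.6 describes the later contact: "Medical Charts will be reviewed to assess if the subject was readmitted within 30 days of discharge". For the withdrawn, "Follow-up phone call and Medical Chart review will instead occur 30 days after withdrawal for patients who are withdrawn prior to discharge".

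Section 8.7.c reports PRN treatments as a median count and as an average per inpatient day. Section 8.7.d compares PRN per patient day (robust Poisson), length of stay and rehospitalisation (Wilcoxon rank sum) with the historical cohort. Section 8.7.e adds: "Missing data will not be imputed or carried forward in any of the analyses", and bases continuous summaries on subjects with data. No analysis set is defined; ITT appears only in the abbreviation list. Section 3.c describes the 60 historical charts without mentioning any removal of patients who worsened.

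**The concern.** Two of the three triggers are escalations of care, so who leaves the study depends on how the patient fares. The primary objective is the PRN requirement of patients hospitalised with an exacerbation, and length of stay is a secondary objective. For the patients who do worst, neither quantity has a stated data source after withdrawal or a stated place in the analysis. Under the same text a site could cut their records at withdrawal, drop them, or follow them to discharge by chart, and the three choices give different results.

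Readmission is affected too. It is the grouping variable in Sections 8.7.c and 8.7.d and an outcome in the historical comparison, yet the withdrawn are assessed on a clock that starts at withdrawal.

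The BiPAP text is uneven. A home user whose settings change is withdrawn. A first start of BiPAP after hospitalisation is listed as an exclusion, but the withdrawal wording does not cover a first start after enrolment. Whether that patient's data stay in depends on how the site reads the item.

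**Working it through.** **Step 1: the plan's own figures.** Section 4.a: 120 approached × 2/3 = 80 enrolled, which reproduces. Expected 30-day follow-up: 80 × 0.80 = 64. No in-hospital withdrawal rate is given, so the size of any bias cannot be derived. All inputs in Steps 2 to 4 are assumptions, as are the days in Step 5.

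**Step 2: length of stay.** Assume a stay of 4 days if not withdrawn and 9 days if withdrawn, with withdrawal on day 2. For a fraction f withdrawn:

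- followed to discharge: 4(1 − f) + 9f
- cut at withdrawal: 4(1 − f) + 2f
- dropped: 4

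| f | Followed | Cut | Dropped |
|---|---|---|---|
| 5% | 4.25 | 3.90 | 4.00 |
| 10% | 4.50 | 3.80 | 4.00 |
| 15% | 4.75 | 3.70 | 4.00 |
| 20% | 5.00 | 3.60 | 4.00 |

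Cutting always shortens the mean. Dropping shortens it if the withdrawn truly stay longer.

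**Step 3: PRN use at 10% withdrawn (8 of 80).** Assume 2 treatments/day in the 72 others, and in the withdrawn 4/day for 2 days, then r/day for the remaining 7.

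- Total per patient, followed: [72×4×2 + 8×(2×4 + 7r)]/80 = (640 + 56r)/80. Cut: 640/80 = 8.0. Dropped: 576/72 = 8.0.
- Pooled rate (all treatments over all days), followed: (640 + 56r)/360. Cut: 640/304 = 2.11. Dropped: 576/288 = 2.00.
- Mean of per-patient rates, followed: [72×2 + 8×(8 + 7r)/9]/80. Cut: (72×2 + 8×4)/80 = 2.20. Dropped: 2.00.

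| r after withdrawal | Total, followed (cut 8.0, dropped 8.0) | Pooled rate, followed (cut 2.11, dropped 2.00) | Mean rate, followed (cut 2.20, dropped 2.00) |
|---|---|---|---|
| 4 | 10.8 | 2.40 | 2.20 |
| 2 | 9.4 | 2.09 | 2.04 |
| 1 | 8.7 | 1.93 | 1.97 |
| 0 | 8.0 | 1.78 | 1.89 |

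The total is understated, or unchanged when r = 0. Cutting can never raise it. Dropping would raise it only if the withdrawn had fewer treatments over their whole stay than the others. The per-day rate has no fixed direction: at r = 4 the pooled rate looks better than it is (2.11 or 2.00 against 2.40), and at r = 1 it looks worse (2.11 or 2.00 against 1.93).

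**Step 4: length of stay against the historical cohort.** Simulation of 10,000 runs with 80 study and 60 historical patients, no true difference, and no removal from the historical group. Stays are lognormal with medians of 4 and 9 days and log-SD 0.5; withdrawal is on day 2; the test is a two-sided 0.05 Wilcoxon rank sum. False-positive rates:

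| f | Followed | Cut | Dropped |
|---|---|---|---|
| 5% | 4.8% | 12.2% | 6.2% |
| 10% | 5.0% | 34.1% | 11.7% |
| 15% | 5.1% | 63.1% | 19.2% |
| 20% | 4.9% | 85.9% | 30.5% |

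Nearly all of those in the last two columns favour the study cohort. Medians move less than means: at 10% cut, −0.52 against −0.82 days; at 10% dropped, −0.25 against −0.57.

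**Step 5: readmission clock.** A patient withdrawn on day 2 and discharged on day 10 is reviewed on day 2 + 30 = 32. That covers 32 − 10 = 22 days after discharge, against 30 for other patients.

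**The case against.** The strongest reply is that the documents never say collection stops. Section 5.2.4 runs from enrolment to discharge, Section 5.1 follows subjects to 30 days after discharge, and Section 5.2.6 has the chart opened after withdrawal. A reader might infer that PRN and length-of-stay data end at withdrawal, but the text is silent. That reply stands: the defect is that nothing provides for these data, not that the plan forbids them.

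A reader might also infer that both endpoints must look better than they are. Step 3 does not support this for PRN per inpatient day, which is part of the primary analysis and the PRN measure used against the historical cohort. With a constant 4/day and records cut at withdrawal, the mean of per-patient rates is not biased at all (2.20 either way).

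Nor is escalation of care simply hidden. Section 2.d lists AEs and SAEs among the endpoints. The seriousness criteria in Section 6.2 would catch many critical care transfers. Withdrawal is a CRF item in Section 5.2.5, and Section 6.4 records further SARS-CoV-2 results. What remains is that no efficacy endpoint counts these events.

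Section 3.c is a short summary, so its silence does not prove that the 60 charts include such patients. The study is also single-arm with no power claim, and an on-treatment estimate would be a legitimate target for patients receiving the regimen. The plan does not say that it chose one, however.

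Finally, keeping patients in the study has a side effect. Section 7.2 bans certain inhaled drugs for the duration of the study, while Sections 4.b.ii and 6.4 send withdrawn patients to the hospital's usual care. This stands, and the fix has to deal with it.

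**Conclusion.** The point holds. A stated rule takes patients out of the study partly because they got worse, and nothing says how their PRN counts and discharge date are then obtained or analysed. Combined with analysis of non-missing data only, this likely understates length of stay. It leaves total PRN count understated or unchanged, provided the withdrawn use at least as many treatments over their whole stay as the others. PRN per inpatient day may be biased in either direction.

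The size is unknown. Under the assumptions in Step 2, at 10% withdrawn, mean stay is understated by 0.50 days if these patients are dropped (4.00 against 4.50) and by 0.70 if they are cut (3.80 against 4.50). The historical comparison may be biased towards the study cohort, but only if the 60 charts include patients who worsened. Claims that data collection definitely ends, or that every PRN measure is flattered, go beyond the text.

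**What to change.** Leave the care rules as they are and amend the data and analysis text.

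- In Section 4.b.ii, the synopsis and Section 6.4, state that a patient who meets a withdrawal trigger stays in follow-up for data collection unless consent is withdrawn.
- In Section 5.2.6, list what is taken from the chart already being reviewed: PRN treatments with times, actual discharge date, readmission within 30 days of that discharge, and vital status. Time the review so that it covers those 30 days.
- In Section 8.7, define the set for the primary and length-of-stay analyses as all enrolled and treated patients. Add a secondary on-treatment summary cut at the event, and report the number withdrawn by reason.
- Check whether the 60 historical charts include such patients, and apply the same rule to both cohorts.
- Reconcile the Section 7.2 ban with the usual care allowed in Sections 4.b.ii and 6.4, and reconcile the BiPAP wording for new initiation against changed settings. The clinical content is for the investigators to settle.

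The cost is a wording amendment and a few extra chart abstractions. The downside is that the main figures will include some time off study drug, which the on-treatment summary separates out.

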## 5. STUDY VISITS AND ACTIVITIES

### 5.1 DESIGN

This is a single-center, phase IV, post market approval prospective, open-label study evaluating outcomes of TRELEGY ELLIPTA (fluticasone furoate 100 mcg, umeclidinium 62.5 mcg, and vilanterol 25 mcg inhalation powder) on PRN nebulized short-acting beta agonist (SABA) treatment in hospitalized subjects with COPD with or without asthma.

Approximately 80 adult subjects with COPD with or without asthma will take part in this study at Baylor University Medical Center. Subjects will be given TRELEGY ELLIPTA, using the Ellipta device, placed on a consistent short-term systemic corticosteroid therapy, and followed until 30 days post hospital discharge. This study will not include patients with rapidly deteriorating or potentially life-threatening episodes of COPD or asthma.

### 5.2 STUDY VISITS

#### 5.2.1 PRE-SCREENING

The inpatient hospital team will identify and refer the potential subject to the study team. The study team will verify that all inclusion criteria and none of the exclusion criteria are met.

#### 5.2.2 SCREENING (+ 24 hours)

Subjects will be identified from the inpatient hospital team. Prior to participation in the study, each subject will be given an opportunity to ask questions and to understand the details of study participation, including risks and benefits. The consent process will be documented in the subject's source documents.

#### Assessments and procedures at screening

- Informed consent
- Assignment of screening number
- Inspiratory Flow Rate (PIFR) evaluation, with InCheck DIAL device set to measure medium low resistance. The best of 3 maximum inspiratory flow measurements, taken from RV will be recorded.
- Spirometry (FEV1, FVC, FEV1/FVC)
- Inclusion/Exclusion Criteria
- Demographics
- Medical History
- Decision by investigator to enroll subject or to declare screen failure.

#### **5.2.3 ENROLLMENT (within 24 hours of admission)**

The following procedures/assessments will be done the morning or following morning of admission into study:

- Concomitant Medications
- Adverse Events (AE) Assessment
- Patient Satisfaction Questionnaire (St George's Respiratory questionnaire-short version)

In addition, data from the specified assessments will be collected when available, and entered the case report forms (CRFs):

- Vital signs

- Physical Exam

#### **5.2.4 TREATMENT (Enrollment to Discharge)**

TRELEGY ELLIPTA (fluticasone furoate 100 mcg, umeclidinium 62.5 mcg, and vilanterol 25 mcg inhalation powder) will be initiated on the morning of enrollment if feasible, or the morning after enrollment otherwise. Treatment will continue daily until discharge. Treatments will be administered by a respiratory therapist daily in the morning between 06:00 AM and 12:00 PM. Patients will receive nebulized short-acting beta-2 agonist (SABA) treatments of albuterol sulfate (2.5mg) as needed during hospitalization. Patients will receive prednisone 40 mg PO daily for the first 7 days from enrollment, subtracting 1 day for each consecutive day the patient received systemic corticosteroid treatment prior to enrollment.

Treatment procedures/assessments include:

- Concomitant Medications
- AE Assessment
- TRELEGY administration

Data from the following specified assessments will be collected daily, when available, and entered the case report forms (CRFs):

- Vital Signs
- Short-acting beta agonist (SABA) therapy: number and time of treatments

